#### STUDY BASICS

#### 1. \* 3.1 Title of study

Evaluation of the Implementation of PrEP Provision for Ugandan Fisherfolk

2. \* 3.2 Brief summary or abstract. Note: this was populated from question 1.1c on the prescreener. Using this information please provide a brief summary or abstract of the study. Describe its purposes, study methods (i.e., participants, procedures, data sources), and expected results.

Please note that this is a transfer from RHINO 1.0, ID 2019-0571

Worldwide, fisherfolk are at an exponentially higher risk for HIV than the general population in their regions. In Ugandan fisherfolk communities, HIV prevalence is estimated to be 15-40% - much higher than in the general Ugandan population, for which HIV prevalence is estimated to be 5.9% among those aged 15-49. It is estimated that fisherfolk represent 5% of the population, and about 10% of the labor force is involved in the fisheries sector; fishing regions (lakes, rivers, etc.) cover about 20% of Uganda. Fisherfolk include fishermen and their families, people who support the fish trade business (e.g., fish vendors, boat off loaders), and commercial sex workers (CSWs) who live in fishing communities. A previous RAND study (led by [name]) with Makerere University School of Public Health, and Mildmay Uganda tested home-based and event-based antiretroviral therapy (ART) distribution models. This study will build on the previous findings and apply them to the development and testing of two PrEP delivery models for high-risk HIV-negative fisherfolk following HIV testing.

We propose to explore the acceptability and feasibility of PrEP, and to develop and compare the implementation of two interventions to promote PrEP use among fisherfolk: community-based vs. healthcare facility-based PrEP provision. We will partner with the Ministry of Health throughout the project, regularly meeting with its PrEP Technical Working Group to discuss study results and determine next steps for policy and national implementation.

The Specific Aims are:

- 1. To conduct formative qualitative research to examine barriers to and facilitators of PrEP uptake, and to obtain input on acceptable PrEP messaging and provision, for fisherfolk communities on Lake Victoria, Uganda.
- 2. To conduct a mixed-methods analysis comparing the implementation of community-based vs. healthcare facility-based PrEP provision for fisherfolk communities on Lake Victoria, Uganda. When this study was initially proposed, the intent was to purchase and supply PrEP to study participants as it was not widely used in the country as a whole, or in fishing communities. Since the study was funded, PrEP use has become more widespread in Uganda and is provided by Mildmay Uganda via a Ugandan Ministry of Health program. As a result, the study will no longer purchase and provide PrEP through the grant, and instead will evaluate enhancements (i.e., behavioral interventions) to the standard of care for providing PrEP in Ugandan fishing communities.

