At Nakiwogo, events will be held in a public temporary space (e.g., tent, church) in partnership with Entebbe Hospital, and at Kigungu, Mildmay staff will use space in the nearby public Kigungu Health Center III to test and treat clients during community mobilization events. In Nakiwogo only, we will conduct an enhanced behavioral PrEP intervention to compare to the standard of care in Kigungu. Specifically, in Nakiwogo, we will have a three-pronged intervention: 1) During healthcare outreach events in Nakiwogo, we will conduct PrEP workshops, in which people who want to know more about PrEP can learn basic facts about PrEP and also can be taught skills about how to advocate for PrEP in their community. These PrEP workshops will be conducted by master trainers, who are Mildmay staff who have been trained by the Ugandan Ministry of Health to conduct health workshops and trainings. 2) Check-in Calls: To support PrEP adherence, healthcare workers will call PrEP users regularly (e.g., every 1-2 weeks), to check in about any questions and to remind them of the next date and place to pick up refills. Calls will be more frequent after PrEP initiation, to ask about side effects. 3) To support PrEP adherence, healthcare workers will encourage PrEP users to select an adherence supporter, who is a family member or friend to whom they disclose their PrEP use. The adherence supporter agrees to remind them to adhere to PrEP and get refills. Healthcare workers will ask the PrEP user for the name and contact information, as well as the age and gender, for the adherence supporter, so that the adherence supporter can be contacted to remind them about refills, as well as if the PrEP user does not show up for a refill. All Adherence Supporters will also be invited to the intervention workshop, which is open to all community members. Note that the first intervention component (PrEP workshop) will be adapted from our current work in Uganda on prevention advocacy among people living with HIV (2016-0227; 2021-N0155). The last two intervention components are standard practices for people living with HIV on antiretroviral treatment, and will be adapted for PrEP users; provider guidance for adherence supporters will also be adapted from our current work in Botswana (2019-0253). To train master trainers and healthcare

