providers for the intervention, we have modified Ugandan Ministry of Health PrEP training slides for healthcare providers and counselors, tailoring them based on the Phase 1 formative work and adding issues of importance to fisherfolk communities. We have received permission from the Ugandan Ministry of Health to make these modifications, and we are regularly meeting with the Ugandan Ministry of Health to update them about the study, and to help develop the intervention.

Per their usual Ministry of Health compliant procedures for PrEP, Mildmay healthcare providers will use an assumed consent procedure for providing PrEP. That is, individuals who attend an HIV testing event at which PrEP is being provided are assumed to consent to being prescribed PrEP when appropriate per Uganda Ministry of Health guidelines. Mildmay providers will draw blood to screen for PrEP contraindications [HIV-1 infected or evidence of possible acute HIV infection; allergy to Tenofovir Disoproxil Fumarate (TDF) and/or Emtricitabine (FTC); poor renal function; unwilling/unable to return for 3-monthly HIV testing, counseling and safety monitoring visits; weight <35kg]. Those eligible can obtain PrEP during Mildmay's outreach events, either in a temporary community-based venue at Nakiwogo, at Entebbe Hospital near Nakiwogo, or at Kigungu Health Centre III. Per Ministry of Health guidelines, most fisherfolk are eligible for PrEP as members of a high risk key population (with a high prevalence of multiple partners, transactional sex, alcohol use/abuse, serodiscordant relationships, and inconsistent condom use).

Update: After completion of the intervention in the intervention site, Nakiwogo (in Sept 2022), the implementing partner will provide the intervention to the comparison site, Kigungu. We will continue to collect de-identified PrEP user data to evaluate implementation at the comparison site.

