#### **Part 8: Conclusion**

1. \* 8.1 Does the proposed study involve any ethical issues not already discussed in the study application?

Yes No

2. 8.2 Please enter any other comments or information that you would like to share with the HSPC reviewer that would be relevant to the review.

It should be clarified that the intervention test is of the different implementation modes of PrEP provision (a behavioral intervention), rather than testing the effectiveness of PrEP (a biomedical intervention). This application notes the risks of PrEP (e.g., side effects) as part of the

intervention, although such risks are not expected to be related to the behavioral intervention.

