## **Statistical Analysis Plan**

Analyses will compare data from before the intervention to during the intervention period. Separate logistic regression models will be used to predict the likelihood of PrEP persistence (i.e., PrEP possession at 6-months and PrEP possession ratio of >80% in 6-months) with a time indicator (before vs. during the intervention). PrEP user age and gender will be included as covariates. If PrEP persistence is 0% at follow-up, logistic regression, which allows cannot be used as the odds ratio would be undefined. Thus, in this case, Fisher's Exact test will be used to evaluate change in the persistence outcome.

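### Aim 2 keeps a community-versus-facility comparison beside its replacement, and the SAP estimates neither that comparison nor enhanced Nakiwogo against standard-of-care Kigungu

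*Combined protocol and SAP*

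**What the plan says.** Three parts of the document describe the comparison differently.

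- **The aim.** The summary in section 3.2 proposes to "compare the implementation of two interventions to promote PrEP use among fisherfolk: community-based vs. healthcare facility-based PrEP provision". Aim 2 repeats this as "comparing the implementation of community-based vs. healthcare facility-based PrEP provision". The Aim 2 paragraph then explains that the study no longer buys PrEP and "instead will evaluate enhancements (i.e., behavioral interventions) to the standard of care for providing PrEP in Ugandan fishing communities". The comments in section 8.2 add that "the intervention test is of the different implementation modes of PrEP provision (a behavioral intervention", in a sentence whose purpose is to distinguish this from a test of PrEP as a drug.
- **The design.** Section 5.10a says that at Nakiwogo "events will be held in a public temporary space (e.g., tent, church) in partnership with Entebbe Hospital", while at Kigungu space in the public Health Center III is used. Eligible clients can obtain PrEP "either in a temporary community-based venue at Nakiwogo, at Entebbe Hospital near Nakiwogo, or at Kigungu Health Centre III". The workshops, check-in calls and adherence supporter are allocated by site: "In Nakiwogo only, we will conduct an enhanced behavioral PrEP intervention to compare to the standard of care in Kigungu". An update in 5.10a and 5.14b has the implementing partner deliver the package at Kigungu once Nakiwogo finishes in September 2022.
- **The analysis.** The SAP fits separate logistic models for the persistence outcomes "with a time indicator (before vs. during the intervention"), with age and gender as covariates. Fisher's exact test is the fallback if persistence is 0% at follow-up. The SAP names neither site and has no site, venue or site-by-period term.

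**The concern.** A reader who takes section 3.2 at its word expects an answer on where PrEP should be delivered. The design varies three things together between the sites in the main period: the landing site itself, the event venue and the behavioural package. If persistence were better at Nakiwogo, the stated aim invites the conclusion that community venues work better, when the package, or some difference between the two communities, could have produced the result.

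The SAP does not correct this. A before/during contrast carries no information on venue, and without a site-by-period term it does not compare the package with standard of care at the other site either. Section 3.7 says that the results will feed recommendations for Ministry of Health policy, so which comparison the trial can support is a practical matter.

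**Working it through.** The documents give no alpha, power, effect size or sample-size calculation, so there is no planned figure to reproduce. The check is whether each effect can be estimated. An effect is estimable only if its contrast lies in the row space of the design matrix.

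**Inputs.** Event venue by site: 5.10a and 5.10e. Package allocation and the later roll-out: 5.10a and 5.14b. Pick-up points: 5.10a. Model terms: SAP. One assumption is needed. The documents give venues prospectively, and for existing events 6.11a does not say which site used which kind of venue. The pre-period venue is therefore taken to be the same as the planned one.

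**Step 1, main period.**

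| Cell | Intercept | Nakiwogo | Community venue | Package | During |
|---|---|---|---|---|---|
| Nakiwogo before | 1 | 1 | 1 | 0 | 0 |
| Nakiwogo during | 1 | 1 | 1 | 1 | 1 |
| Kigungu before | 1 | 0 | 0 | 0 | 0 |
| Kigungu during | 1 | 0 | 0 | 0 | 1 |

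The site and venue columns are identical. Five columns have rank 4, and venue is not estimable. The package is estimable, but only as (Nakiwogo during − Nakiwogo before) − (Kigungu during − Kigungu before), which is the site-by-period term. With one site per delivery model, the site-level contrast has 2 − 2 = 0 residual degrees of freedom.

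If the temporary venue at Nakiwogo had instead begun together with the package, the venue column would read 0, 1, 0, 0. That equals the package column, so venue would be aliased with the package and still not be estimable.

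**Step 2, add the later Kigungu roll-out.** A third-period cell for Kigungu with the package gives 5 cells, 6 columns and rank 5. Adding a third-period Nakiwogo cell without the package gives 6 cells, 6 columns and still rank 5. Site and venue remain identical columns in both.

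**Step 3, split Nakiwogo by place of pick-up.** Separating the temporary venue from Entebbe Hospital gives 6 cells, 5 columns and rank 5. Venue is now algebraically estimable. All of that information comes from within Nakiwogo, where the documents describe no assignment of clients to a pick-up point, and no such analysis is planned.

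**Step 4, the SAP model.** Its columns are intercept, time, age and gender: 4 columns, rank 4. None of them is venue or site, and there is no interaction. It returns a before/during change and nothing else.

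**The case against.** The strongest reply is that the change of objective is already on the page. The Aim 2 paragraph says why PrEP is no longer supplied and redirects the study to enhancements. Section 5.10a puts that into operation, and the participant tasks in 5.10f are the package. Section 8.2 uses loose words about modes of provision but labels the test behavioural. A reader might infer that the sponsor changed the question without saying so. The documents do not support that: the venue wording is text left standing beside its replacement. It is nonetheless current text, in both the summary and the aim.

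A reader might also infer that venue and site are perfectly collinear, so that no data could ever separate them. That goes too far. Entebbe Hospital is a pick-up point for Nakiwogo, and 5.14b extracts refill locations from medical records, so a contrast within Nakiwogo is possible (step 3). It is self-selected and unplanned, and the larger de-identified extract lists only refill dates and durations, so it does not answer Aim 2. Nor do the documents state that venue was constant across periods.

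It would likewise be wrong to say that only one site ever receives the package, because Kigungu does later. Step 2 shows that this does not free venue from site.

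Finally, Aim 2 is mixed-methods, and 6.11a splits the interviews by community. Describing implementation in two settings needs no estimable venue coefficient, and that component stands. It can describe differences between the sites, but it cannot attribute them to venue.

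**Conclusion.** The point holds in a limited form. No planned quantitative analysis addresses the community-versus-facility comparison in section 3.2, and a difference between the sites could not be attributed to venue. Event venue differs only by site, and in the main period the package is added at the same site as the temporary venue. The SAP also does not estimate the comparison that replaced it, enhanced Nakiwogo against standard-of-care Kigungu.

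On the stated layout the deficit is one rank (4 of 5 columns) and 0 site-level degrees of freedom for the delivery model. More participants at the same two event venues would not change either figure. The aliasing of venue with site assumes that pre-period venues matched the planned ones. The finding that the SAP estimates neither between-site comparison needs no assumption, since it follows from the model terms alone.

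This is an aim left partly un-updated and an SAP that does not match it. It can be put right in the text and the analysis plan.

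**What to change.** 1. In the section 3.2 summary, in Aim 2 and in the 8.2 comments, restate the quantitative comparison as the three-part behavioural package against standard of care. Keep the mixed-methods uptake and acceptability components.
2. State that no community-versus-facility effect is estimated, and that any contrast by refill location or between sites in the interviews is descriptive.
3. In the SAP, choose one of two routes. Either add site and site-by-period terms, using the Kigungu records that 5.14b already has extracted, and report the site-by-period term as the package effect. Or name the site and limit the claim to before/during change within it.

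The cost is mostly wording, and no new data collection is needed for the second route. For the first, the larger two-community extract is described as holding no socio-demographic data. The model on that extract would therefore run without the age and gender covariates unless these can be supplied from another source.

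The downside is that the delivery-model claim is given up. With one site per condition, the site-by-period contrast still rests on the assumption that persistence at the two sites would have moved in parallel without the package, and the SAP should say so.

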#### **Protocol Documents:**

Document	Category	Date Modified	Document History	
rmi ·				

There are no items to display

8. \* 3.6 Has this project already had a scientific review-that is, a review of the adequacy of the study design? Check all that apply.

Yes - by funder's proposal review committee

9. 3.7 Who is the intended audience for the results of this study? Where and in what form will you disseminate results?

#### \* Who is the intended audience for the results of this study:

Our findings will be important in informing researchers and key stakeholders, including healthcare providers and policymakers, about barriers to implementation and potential solutions to address barriers suggested by stakeholders. Throughout the study, we will meet with Ugandan Ministry of Health policymakers to keep them apprised of the study goals and preliminary and final results, and to obtain their input on the PrEP intervention protocols. Importantly, we will engage with policymakers prior to the pilot intervention, to discuss the qualitative results and together determine the pilot intervention protocol, and we will engage with them throughout the pilot intervention implementation, in order to discuss lessons learned, and the brainstorm about how any challenges can be addressed.

#### \* Where and in what form will you disseminate results?

Following the analysis of the qualitative and quantitative data, we will develop a presentation and summary report that will be shared with the Ugandan Ministry of Health, with the goal of obtaining policymaker input into the interpretation of the results, as well as recommendations for policy based on the results.

#### 10. STUDY FUNDING SOURCES

11. \* 3.8 Indicate the primary source of funding whether or not the funding is coming directly to RAND as the prime contractor or grantee. That is, if funding from an agency is being channeled through another organization, check that agency. Check all that apply

Selection	Name
D.	National Institutes of Health (NIH)

#### 13. \* 3.8d Specify the NIH institute:

F. National Institute of Mental Health (NIMH)

14.

#### 15. RESEARCH OVERVIEW - DATES

The dates below should cover the entire project and all population-procedure study components. Please provide the dates below based on your best estimates at this time. These dates should be taken from the contract, grant, or statement of work when possible.

#### **Start Dates**

- 16. \* 3.9 Project Start Date. Grant and non-FFRDC research should use the award date as the project start date. FFRDC research should use the date on which the project task number was opened. Pick the best date you can and if necessary use the text field below to explain any uncertainties. Enter dates in the following format: mm/dd/yyyy. 4/1/2020
  - \* 3.9a Please explain any date uncertainties below, if applicable.
- 17. \* 3.10 Anticipated Data Acquisition Start Date. (*Note: this should include pilot/pretest activities*). Pick the best date you can and if necessary use the text field below to explain any uncertainties. Enter dates in the following format: mm/dd/yyyy.
  - \* 3.10a Please explain any date uncertainties below, if applicable.

#### 18. End Dates

\* 3.11 Anticipated Data Acquisition End Date. Pick the best date you can and if necessary use the text field below to explain any uncertainties. Enter dates in the following format: mm/dd/yyyy.

11/30/2023

- \* 3.11a Please explain any date uncertainties below, if applicable.
- 19. \* 3.12 Project End Date. Pick the best date you can and if necessary use the text field below to explain any uncertainties. Enter dates in the following format: mm/dd/yyyy. 3/31/2024

## RESEARCH OVERVIEW - EXTERNAL ORGANIZATIONS COLLABORATING IN THE RESEARCH

This section of the study form asks questions about other institutions that are participating in human subjects research for this study. All institutions participating in the research must undergo human subjects review either by the institution's own institutional review board (IRB - the HSPC is RAND's IRB) or by deferring to the IRB of another institution (including RAND).

- \* 3.13 Are there other institutions besides RAND involved in this study? Yes No
- 20. \* 3.13a Are you suggesting that RAND should defer to another institution's IRB for this study?

Yes No

- \* 3.13a1 Is RAND the only direct recipient of funding for this project? Yes
- 21. \* 3.13a3 Which institution is the prime contractor or grantee?
- 22. List each institution involved in any aspect of this study. Click the Add button below to add an institution and fill in all of the required information for that institution. Repeat for each institution. Check with each institution listed whether they have a Federalwide Assurance (FWA).

## **External Organizations:**

Name	Involved Activities	FWA Available?
Makerere University School of Public Health	Obtaining informed consent Collecting data (surveys, interviews, focus groups, record abstraction, observations, biometric measurements, etc) Receiving identifiable person-level data	Yes
Mildmay Uganda	Obtaining informed consent Collecting data (surveys, interviews, focus groups, record abstraction, observations, biometric measurements, etc) Receiving identifiable person-level data	Yes
University of Illinois Urbana Champagne	Sharing responsibility for research design, data analysis, and/or interpreting and reporting results	No

23. \* 3.13i How do you think IRB review should be conducted for this project? RAND HSPC will review your suggested approach and consult with you if needed to make a decision. By RAND HSPC as Single IRB/IRB of record

24.

**25.** 

26.

2=	Th.	• 4	- 1	
27.	Proi	orieta	rv I	ata

28.	* 3.17 Could the research involve proprietary information (i.e., trade or business
	information that belongs to an organization)? Note RAND has policies regarding the
	handling of proprietary information. Please review the policies on the intranet page before
	acquiring any such information.

Yes	
No	
Don't	know

